2. INTRODUCTION

The respiratory syncytial virus (RSV) vaccine that will be evaluated in this study, the Ad26/protein preF RSV vaccine (VAC18193), is a combination of 2 vaccine components, administered as single intramuscular (IM) injection:

- Ad26.RSV.preF (JNJ-64400141), a replication-incompetent adenovirus serotype 26 (Ad26) containing a DNA transgene that encodes the prefusion conformation-stabilized F protein (pre-F) derived from the RSV A2 strain.
- RSV preF protein (JNJ-64213175), a recombinant pre-F protein derived from the RSV A2 strain.

For the most comprehensive nonclinical and clinical information regarding the Ad26/protein preF RSV vaccine, refer to the latest version of the Investigator's Brochure (IB) for Ad26/protein preF RSV vaccine (IB Ad26/protein preF RSV vaccine 2021).

The term "study vaccine" used throughout the protocol refers to the Ad26/protein preF RSV vaccine as defined in Section 6.1.

The term "sponsor" used throughout this document refers to the entities listed in the Contact Information page(s), which will be provided as a separate document.

2.1. Study Rationale

The aim of this study is to demonstrate the non-inferiority in terms of humoral immune responses of Ad26/protein preF RSV vaccine lots representing key stability indicating critical quality attributes (eg, potency of Ad26.RSV.preF, purity of RSV preF protein) halfway ("intermediate shelf-life") and at the end of the intended shelf-life ("end of shelf-life") in comparison to a non-aged Ad26/protein preF RSV vaccine lot. Demonstrating non-inferior humoral immune responses of material at "intermediate shelf-life" and at "end of shelf-life" to near release material will allow to infer efficacy throughout the vaccine shelf-life.

2.2. Background

RSV is an important cause of serious respiratory infections in adults aged 60 years and older, immunocompromised individuals, and those with underlying chronic cardiopulmonary conditions (Falsey 2005). Exact numbers on the burden of RSV disease in adults aged 60 years and older are limited. In long-term care facilities, RSV is estimated to infect 5% to 10% of the residents per year with significant rates of pneumonia (10%-20%) and death (2%-5%) as a consequence (Falsey 2000). In the United States (US), approximately 177,000 hospital admissions and approximately 10,000 to 14,000 deaths per year are due to severe RSV infections in adults aged 65 years and older (Falsey 2005). These data support the importance of developing a safe and effective vaccine for certain adult populations, such as older adults. Currently, no vaccines or specific treatments are available for RSV.

Several studies have indicated that high levels of serum neutralizing antibodies are associated with a reduced risk of severe RSV infection in older adults (Falsey 1998; Walsh 2004). There is some indication that decreased protection against RSV in older adults could be attributed to an agerelated decline in RSV-specific T-cell function (de Bree 2005; Looney 2002). The Ad26.RSV.preF vaccine component evaluated in this study is based on the AdVac® platform, which has been shown to promote strong humoral and cellular responses (Barouch 2013; Barouch 2018; Data on file; Milligan 2016).

Nonclinical Studies

For the most comprehensive nonclinical information regarding the Ad26/protein preF RSV vaccine, refer to the latest version of the IB for Ad26/protein preF RSV vaccine (IB Ad26/protein preF RSV vaccine 2021).

Clinical Studies

For the most comprehensive clinical information regarding the Ad26/protein preF RSV vaccine, refer to the latest version of the IB for Ad26/protein preF RSV vaccine (IB Ad26/protein preF RSV vaccine 2021).

Clinical Safety Experience with Ad26-based Vaccines

The Janssen Adenoviral Vaccine (AdVac) Safety Database Report (version 6.0; AdVac Safety Database 2021) contains pooled safety data of the following Ad26-based vaccine candidates: Ad26.ZEBOV (Ebola virus), Ad26.ENVA.01, Ad26.Mos.HIV, and Ad26.Mos4.HIV (HIV), Ad26.CS.01 (malaria), Ad26.RSV.FA2 and Ad26.RSV.preF (RSV), Ad26.Filo (filovirus), Ad26.ZIKV.001 (Zika virus), and Ad26.HPV16 and Ad26.HPV18 (HPV). Data from all studies for which the database had been locked for either the interim, primary, or final analysis for which the sponsor has been fully unblinded are included in the AdVac Safety Database Report, ie, 32 completed and ongoing unblinded clinical studies (cutoff date of 31 December 2020). In total, 8,826 participants were vaccinated with an Ad26-based vaccine. Of these 8,826 participants, 8,152 participants (in all 32 studies) were adults, and 674 participants (in 3 studies) were children.

The report also provides a high-level overview of all clinical study SAEs and vaccine exposure during pregnancy cases reported in the Janssen Global Safety Database that also includes all ongoing (open-label and blinded) studies, non-Janssen sponsored studies, and mass vaccination campaigns which are not integrated in the AdVac Safety Database Report. This data set includes also SAEs and pregnancy cases of Ad26.COV2.S (Janssen COVID-19 vaccine) vaccine clinical studies. About 200,000 participants were dosed with an Ad26-based vaccine at the cutoff date of 31 December 2020.

No significant safety issues have been identified from the data available in the current adenoviral vaccine safety database. Overall, the Ad26-based vaccines were well tolerated, without significant safety issues identified.

Thrombosis With Thrombocytopenia Syndrome

Thrombosis in combination with thrombocytopenia (thrombosis with thrombocytopenia syndrome [TTS]), in some cases accompanied by internal bleeding, has been observed very rarely following vaccination with the Janssen COVID-19 (Ad26.COV2.S) vaccine. Reports include severe cases of venous thrombosis at unusual sites such as cerebral venous sinus thrombosis (CVST), splanchnic vein thrombosis and arterial thrombosis, in combination with thrombocytopenia. The associated symptoms began approximately 1 to 2 weeks after vaccination, mostly in women under 60 years of age. Thrombosis in combination with thrombocytopenia can be fatal. The exact pathophysiology of TTS is unclear. This event has not been observed to date with any other Janssen Ad26-based vaccines. Participants should be instructed to seek immediate medical attention if they develop symptoms such as shortness of breath, chest pain, leg swelling, persistent abdominal pain, severe or persistent headaches, blurred vision, skin bruising or petechiae beyond the site of vaccination.

2.3. Benefit-Risk Assessment

More detailed information about the known and expected benefits and risks of the Ad26/protein preF RSV vaccine may be found in the IB for Ad26/protein preF RSV vaccine (IB Ad26/protein preF RSV vaccine 2021).

2.3.1. Risks Related to Study Participation

The following potential risks for the Ad26/protein preF RSV vaccine will be monitored during the study:

Risks Related to Ad26/protein preF RSV Vaccine

The Ad26/protein preF RSV vaccine is currently being studied in 4 ongoing studies in more than 6,500 participants aged 60 years and older, including participants with comorbidities, to assess safety and immunogenicity and to investigate whether the vaccine prevents RSV disease. In these studies, the most commonly reported solicited local adverse events (AEs) were injection site pain/tenderness and swelling (mild to moderate). The most frequently reported solicited systemic AEs were fatigue, muscle pain, headache, chills, joint pain, and nausea, which were mild to moderate in severity. These solicited AEs were short-lived and resolved within a few days. Overall, available results from these studies show the vaccine to be well-tolerated with no safety concerns.

General Risks Related to Vaccination

In general, IM injection may cause local itching, warmth, pain, tenderness, erythema/redness, induration, swelling, arm discomfort, or bruising of the skin. Participants may exhibit general signs and symptoms associated with IM injection of a vaccine, including fever, chills, rash, myalgia, nausea/vomiting, headache, dizziness, arthralgia, general itching, and fatigue. These side effects will be monitored, but are generally short-term and do not require treatment.

Syncope can occur in association with administration of injectable vaccines. Syncope can be accompanied by falls. Procedures should be in place to avoid falling injury. If syncope develops,

participants should be observed until the symptoms resolve. Fear of injection might lead to fainting and fast breathing.

Participants may have an allergic reaction to the vaccination. An allergic reaction may cause a rash, urticaria, or even anaphylaxis. Severe reactions are rare. Participants with a known or suspected allergy, or with a history of anaphylaxis or other serious adverse reactions to vaccines or their excipients (including specifically the excipients of the study vaccine), will be excluded from the study.

After vaccination, participants will remain at the study site for at least 15 minutes and will be closely observed by study staff. Necessary emergency equipment and medications must be available in the clinic to treat severe allergic reactions.

Pregnancy and Birth Control

The effect of the Ad26/protein preF RSV vaccine on a fetus or nursing baby is unknown. Participants may therefore only participate if they are postmenopausal (defined as no menses for 12 months without an alternative medical cause) and not intending to conceive by any methods. Participants who are surgically sterile are also eligible for the study. Follow-up information regarding the outcome of the pregnancy will be required.

Because the effect on sperm is unknown, participants must inform the study-site personnel if their partner becomes pregnant during the study. Follow-up information regarding the outcome of the pregnancy will be requested upon the consent provided by the partner.

Participants with Immunosuppression/Reduced Immune Response

Participants with abnormal function of the immune system will be excluded from the study. Limited evidence indicates that inactivated vaccines (or nonreplicating viral vaccines) generally have the same safety profile in immunocompromised patients as in immunocompetent individuals. However, the magnitude, breadth, and persistence of the immune response to vaccination may be reduced or absent in immunocompromised persons.

Risks from Blood Draws

Blood draws may cause pain, tenderness, bruising, bleeding, dizziness, vasovagal response, syncope, and rarely, infection at the site where the blood is taken. Participants with contraindications to IM injections and blood draws (eg, bleeding disorders) will be excluded.

Concomitant Vaccination

Concomitant vaccination might have an influence on both the safety profile and immunogenicity of the Ad26/protein preF RSV vaccine. Likewise, the Ad26/protein preF RSV vaccine might have an influence on both the safety profile and immunogenicity of any concomitant vaccination. As a result, licensed live attenuated vaccines should be given at least 28 days before or after vaccination. Other licensed (not live) vaccines (eg, influenza, tetanus, hepatitis A, hepatitis B, rabies) should be given at least 14 days before or after vaccination to avoid potential confusion of adverse

reactions and potential immune interference. If a vaccine is indicated in a postexposure setting (eg, rabies or tetanus), it must take priority over the study vaccine.

For Severe Acute Respiratory Syndrome Coronavirus-2 (SARS-CoV-2) vaccines licensed or available under Emergency Use Authorization: live attenuated vaccines should be given at least 28 days before or after vaccination; non-live vaccines should be given at least 14 days before or after vaccination. A viral-vectored SARS-CoV-2 vaccine is not to be given at any time prior to randomization or during the study period until 28 days after study vaccination.

Unknown Risks

There may be other risks that are not known. If any significant new risks are identified, the investigators and participants will be informed.

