2.3.3. Benefit-Risk Assessment of Study Participation

Based on the available data and proposed safety measures, the overall benefit-risk assessment for this clinical study is considered acceptable for the following reasons:

- The dose levels of Ad26.RSV.preF and RSV preF protein used in the current study were determined from the primary analysis of Cohort 2 in study VAC18193RSV1004 and are currently under further evaluation in studies VAC18193RSV1004 and VAC18193RSV2001. Lower dose levels of Ad26.RSV.preF were evaluated in studies VAC18193RSV1004 and VAC18193RSV2005. The available safety data from all studies show the vaccine to be well-tolerated with no safety concerns. For details on the justification for dose levels selected for this study, see Section 4.3. In the primary analysis of study VAC18193RSV2001, vaccine efficacy was demonstrated for these dose levels in adults aged 65 years and above, for the prevention of LRTD caused by RSV.
- Only participants who meet all inclusion criteria and none of the exclusion criteria (specified in Section 5) will be allowed to participate in this study. The selection criteria include adequate provisions to minimize the risk and protect the well-being of participants in the study.
- Safety will be closely monitored throughout the study:

In general, safety evaluations will be performed at scheduled visits during the study, as indicated in the Schedule of Activities.

After vaccination, participants will remain at the study site for at least 15 minutes and will be closely observed by study staff. Necessary emergency equipment and medications must be available in the clinic to treat severe allergic reactions. Participants will use a participant diary to document solicited signs and symptoms. Details are provided in Section 8.2.

The investigator or the designee will document unsolicited AEs, serious adverse events (SAEs), and adverse events of special interest (AESIs) as indicated in Sections 8.2 and 8.3 and Appendix 2.

Any clinically significant abnormalities will be followed by the investigator until resolution or until clinically stable.

After vaccination, participants will enter a 6-month safety follow-up period for collection of SAEs and AESIs.

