5. STUDY POPULATION

Screening for eligible participants will be performed within 28 days prior to the study vaccination or on the day of vaccination.^a Refer to Section 5.4 for conditions under which the repeat of any screening procedures are allowed.

The inclusion and exclusion criteria for enrolling participants in this study are described below. If there is a question about these criteria, the investigator must consult with the appropriate sponsor representative and resolve any issues before enrolling a participant in the study. Waivers are not allowed.

For a discussion of the statistical considerations of participant selection, refer to Section 9.2.

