 - 7.1 received hematopoietic stem cell transplant in medical history, treatment with immunoglobulins expected to impact the vaccine-induced immune response (including monoclonal antibodies for chronic underlying conditions) in the 2 months, immunoglobulins specific to RSV, human metapneumovirus, or parainfluenza viruses in the 12 months, apheresis therapies in the 4 months, or blood products in the 4 months before the planned administration of study vaccine or has any plans to receive such treatment during the study.

Note: The investigator is encouraged to contact the sponsor to discuss eligibility of participants on immunoglobulin treatment.

8. history of TTS or heparin-induced thrombocytopenia and thrombosis (HITT).

- 9. received or plans to receive:
 - a. licensed live attenuated vaccines within 28 days before or after the planned administration of study vaccine.
 - b. other licensed (not live) vaccines within 14 days before or after the planned administration of study vaccine.
- 10. Criterion modified per Amendment 2
 - 10.1 received or plans to receive a SARS-CoV-2 vaccine:
 - a. live attenuated SARS-CoV-2 vaccine within 28 days before or after planned administration of study vaccine.
 - b. non-live SARS-CoV-2 vaccine within 14 days before or after planned administration of study vaccine.
 - c. viral-vectored SARS-CoV-2 vaccine within 6 months prior to randomization or during the study period until 28 days after study vaccination.
- 11. received an RSV vaccine in a previous RSV vaccine study.
- 12. received or plans to receive an Ad26-vectored vaccine at any time prior to randomization until 28 days after study vaccination (this does not apply to SARS-CoV-2 vaccines: for exclusion criteria related to SARS-CoV-2 vaccines, please refer to Exclusion Criterion 10).
- 13. Criterion modified per Amendment 2
 - 13.1 received an investigational drug or used an invasive investigational medical device within 30 days or received an investigational vaccine within 6 months before the planned administration of the study vaccine or is currently enrolled or plans to participate in another investigational study during this study.
 - Note: Participation in an observational clinical study (ie, without intervention) or in the observational phase of interventional studies is allowed upon approval of the sponsor or its delegate.

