6.8. Concomitant Therapy

Prestudy therapies administered within the 30 days before administration of the study vaccine must be recorded on Day 1. Additionally, any history of SARS-CoV-2 vaccination (name/manufacturer of the vaccine and date of administration, whenever possible) prior to and during the study will be collected in the eCRF.

Concomitant therapies associated with solicited AEs will be collected by the participants in the participant diary from the time of study vaccination through 7 days after vaccination. Concomitant therapies associated with unsolicited AEs will be collected and recorded in the eCRF from the time of study vaccination through 28 days after vaccination. Concomitant therapies associated with SAEs or AESIs will be collected and recorded in the eCRF from ICF signature until 6 months after vaccination.

Analgesic/antipyretic medications and non-steroidal anti-inflammatory drugs may be used post-vaccination only in cases of medical need (eg, fever or pain) and their use must be documented. Use of these medications as routine prophylaxis prior to study vaccination is discouraged.

Information on concomitant use of herbal supplements or vitamins will not be collected.

Use of any experimental medication (including experimental vaccines other than the study vaccine) during the study is not allowed.

Vaccination with licensed live attenuated vaccines within 28 days of a study vaccination (ie, before or after) is prohibited. Other licensed (not live) vaccines (eg, influenza, tetanus, hepatitis A, hepatitis B, rabies) should be given at least 14 days before (or at least 14 days after) administration of study vaccine in order to avoid potential confusion of adverse reactions and potential immune interference. If a vaccine is indicated in a post-exposure setting (eg, rabies or tetanus), it must take priority over the study vaccine.

For SARS-CoV-2 vaccines licensed or available under Emergency Use Authorization: live attenuated vaccines should be given at least 28 days before or after vaccination; non-live vaccines should be given at least 14 days before or after vaccination. A viral-vectored SARS-CoV-2 vaccine is not to be given within 6 months prior to randomization or during the study period until 28 days after the last study vaccination.

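### Does the any-time wording on viral-vectored SARS-CoV-2 vaccines in Protocol Section 2.3.1 undermine the 6-month window in Sections 5.2 and 6.8?

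*Protocol*

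**What the plan says.** Three places in the Protocol give a restriction on viral-vectored SARS-CoV-2 vaccination before randomization.

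- Section 2.3.1, under Concomitant Vaccination: "A viral-vectored SARS-CoV-2 vaccine is not to be given at any time prior to randomization".
- Section 5.2, criterion 10.1c, which excludes anyone who received or plans to receive a "viral-vectored SARS-CoV-2 vaccine within 6 months prior to randomization or during the study period until 28 days after study vaccination".
- Section 6.8: "A viral-vectored SARS-CoV-2 vaccine is not to be given within 6 months prior to randomization".

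Three other statements bear on which text decides enrollment. Criterion 12, which restricts Ad26-vectored vaccines in general, adds that "this does not apply to SARS-CoV-2 vaccines: for exclusion criteria related to SARS-CoV-2 vaccines, please refer to Exclusion Criterion 10". Section 2.3.3 says that only people who meet all inclusion criteria and "none of the exclusion criteria (specified in Section 5) will be allowed to participate in this study". Section 5 says that if a question arises about the criteria, "the investigator must consult with the appropriate sponsor representative and resolve any issues before enrolling a participant in the study".

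**The concern.** Section 2.3.1 is current body text, not an entry in the amendment log, and it is phrased as a prohibition rather than as background. Read literally, it covers any earlier viral-vectored SARS-CoV-2 vaccination, however long ago. Criterion 10.1c and Section 6.8 leave out anything more than 6 months back. The same person can therefore be acceptable under one section and not under another.

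Criterion 12 does not explain the difference. It does contain an any-time restriction on Ad26-vectored vaccines, but it takes SARS-CoV-2 vaccines out of its scope and hands them to criterion 10.

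If sites followed different sentences, the enrolled population could differ between sites in previous exposure to a viral vector. The Amendment 2 rationale says that data on interference between consecutive viral-vectored vaccines with different inserts are not yet available, so the exposure is not trivial for an immunogenicity endpoint. A second risk is that someone enrolled in line with criterion 10.1c is later called a protocol deviator on the strength of Section 2.3.1 and loses samples from the Per-protocol Immunogenicity Set.

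**Working it through.** No formula applies. The check is a comparison of the three sections, window by window.

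| SARS-CoV-2 vaccine window | Section 2.3.1 | Section 5.2, criterion 10.1 | Section 6.8 |
|---|---|---|---|
| Viral-vectored, before randomization | any time | 6 months | 6 months |
| Viral-vectored, after study vaccination | 28 days | 28 days | 28 days |
| Live attenuated, before or after | 28 days | 28 days | 28 days |
| Non-live, before or after | 14 days | 14 days | 14 days |

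One row of four differs. The match in the other rows is in the number of days, not word for word. For non-live vaccines, for example, Section 2.3.1 has "non-live vaccines should be given at least 14 days before or after vaccination" and criterion 10.1b has "non-live SARS-CoV-2 vaccine within 14 days before or after planned administration of study vaccine". Section 6.8 counts the 28 days from the last study vaccination, which is the same thing here because only one is given.

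**Who falls in the gap.** Take the time from a viral-vectored SARS-CoV-2 vaccination to randomization.

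- Never vaccinated with one: no section restricts entry.
- 4 months: all three sections restrict entry.
- 8 months: Section 2.3.1 does; criterion 10.1c and Section 6.8 do not.

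The gap is the set vaccinated more than 6 months earlier. Everyone acceptable under Section 2.3.1 on this point is also acceptable under criterion 10.1c, so a site that followed Section 2.3.1 would turn some people away. It would not admit anyone whom criterion 10.1c excludes.

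**Which text sites act on.** Exclusion is defined by the list in Section 5.2. Section 2.3.3 points to Section 5 for participation, and Section 5.3 points to Section 6.8 for prohibited and restricted therapy. Both of these working sections give the same window. The odd sentence sits in the introductory risk discussion.

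**Effect on the primary comparison.** Protocol Sections 9.1 to 9.4 and SAP Sections 2 to 5.3 do not use previous SARS-CoV-2 vaccination in the hypotheses, the 0.67 margin, the ANOVA or the two sensitivity analyses. The exposure precedes randomization, so under double-blind 1:1:1 allocation it is unrelated to group except by chance. The list of major deviations that remove samples is to be final before database lock and unblinding (SAP Section 4). If someone did apply Section 2.3.1 when classifying deviations, that would cost some precision but would not favor one group.

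**The case for a change.** The best argument for acting is that the sentence cannot be waved away as loose prose. It is worded as a rule, and its other windows match the working sections in days. Inclusion criterion 2 asks participants to keep to the restrictions in the Protocol as a whole, not only those in Section 5, and Section 5 allows no waivers. The SAP also plans to tabulate baseline COVID-19 vaccination with a category for the Janssen vaccine (Appendix 2). The Amendment 2 rationale describes that vaccine as Ad26-vectored, so under a literal reading of Section 2.3.1 the category should be empty for vaccination before randomization. Correction would cost only a line of text.

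Much of this stands: the contradiction exists, and no reading makes the two intervals equal. What does not stand is the step from there to a consequence. Criterion 2 concerns willingness to comply and does not set an eligibility window, whereas criterion 10.1c sets one explicitly. The planned table shows that the documents expect such participants to be possible; it does not show that sites were misled. The Amendment 2 rationale also describes a 6-month window, and its change-table row for criterion 10 names Section 5.2 only. That fits a sentence left unaltered elsewhere, although this is an inference. Low cost is a fair reason to tidy the text, but nothing the trial does or concludes would be different afterwards.

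**Conclusion.** The three sections contradict each other on one window and should be reconciled; which interval is clinically right is not judged here. This is a clerical inconsistency, and it calls for no change to the design, the data collected, the sample size or the analysis. Its size is one window of four, limited to people vaccinated more than 6 months before randomization. Their number is not given in the documents and is not estimated.

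The conclusion rests on three assumptions: sites enroll from the criteria in Section 5.2, doubts go to the sponsor as Section 5 requires, and deviations are classified against those criteria before unblinding. If the first failed at some site, the result would be slower recruitment there, not the entry of anyone excluded by criterion 10.1c. If the third failed, some samples might leave the per-protocol set for a reason unrelated to group. Neither would bias the ratio of geometric mean titers between groups.
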